1.2.5.2. Pharmacokinetics of Mogamulizumab

Currently the PK of intravenously administered mogamulizumab has been assessed in 8 clinical studies. The PK results from 6 of the completed studies (0761-EU-001, 0761-0501, 0761-002, 0761-003, 0761-004 and KW-0761-001) are detailed in the mogamulizumab IB.

For the 1.0 mg/kg dose, administered IV (once a week for four weeks then every other week), mean \pm standard deviation (SD) half-life values were 184 ± 64 and 332 ± 86 hrs. on Days 1 and 22, respectively.

1.2.5.3. Immunogenicity of Mogamulizumab

The presence of anti-mogamulizumab antibodies was monitored in studies performed on healthy adults (Study 0761-EU-001) as well as in patients with hematological malignancies (Studies 0761-0501, 0761-002, 0761-003 and 0761-004 and KW-0761-001).

No subjects in these studies had anti-mogamulizumab antibodies detected with the exception of study KW-076-001 in which the analysis, which are still ongoing, reported 4 patients who had positive responses in the pretreatment samples.

CCI

[REDACTED]

[REDACTED]

CCI

[REDACTED]

[REDACTED]

1.2.6. Study Rationale

Tumor metastasis represents the primary cause of mortality in neoplastic patients and remains the major challenge for cancer therapy.

The approach to cancer treatment for metastatic solid tumors, apart from rare exceptions, is mainly palliative and even in patients who present with remarkable responses to cytotoxic or targeted therapies, the disease eventually progresses.

Immuno-oncology therapies have the advantage of being able to mount an ongoing, dynamic immune response that can continue to seek out and kill tumor cells long after the therapy has been given. Thus this adaptive, long-lived response has the potential to completely eradicate tumor cells rather than just lead to a several-log kill.

However, despite recent developments in cancer immunotherapies, clinical benefit occurs in a minority of patients. Only a minority of patients respond to treatment with single agents such as IL-2 for melanoma and kidney cancer,[¹⁹] experimental cancer vaccines such as[²⁰] Provenge® for prostate cancer,[²¹] anti-CTLA-4 monoclonal antibody (mAb) (ipilimumab) for melanoma,[²²] and anti-PD-1 mAbs for multiple indications, with an objective response rate in immunoresponsive tumor types ranging between 16% and 37%. [²³] Recent work has suggested that tumor resistance to immunotherapies might be due to an immunosuppressive status within the tumor microenvironment.

Preclinical experiments demonstrated that when compared with peripheral blood T cells, tumor-infiltrating T cells (TILs) contained a higher frequency of effector Tregs (eTregs), generally characterized by suppressive function. eTreg cells, but not naïve Treg cells, predominantly expressed CCR4 in both cancer tissues and peripheral blood. *In vitro* culture of mogamulizumab with PBMC obtained from cancer patients leads to depletion of CCR4+ Treg and expansion of anti-tumor T cells.[²⁴] *In vivo* evaluation of the effect of CCR4 depletion on anti-tumor immune responses and tumor growth of mogamulizumab has not been performed since appropriate antibodies to murine CCR4 are not available.

[figure not shown]
Of note, preclinical studies have demonstrated that Treg cells expressing the transcription factor FOXP3 play a critical role in suppressing antitumor immune responses.

In vitro or *in vivo* anti-CCR4 mAb treatment selectively depleted eTreg cells and efficiently induced tumor-antigen-specific CD4+ and CD8+ T cells and cytokine production. Thus, cell-depleting anti-CCR4 mAb therapy is instrumental for evoking and enhancing tumor immunity in humans via selectively removing eTreg cells.[²⁵]

The efficacy of 4-1BB agonist as a cancer therapy has been documented. Its therapeutic effects are mediated by enhancing NK and CD8+ T-cell activation and IFN- γ production.

In vivo experiments on a B16-F10 mouse melanoma model demonstrated that the antitumor activity of an anti- 4-1BB can be significantly improved by the combination with an anti-CD4 mAb. When co-administered, anti-4-1BB and anti-CD4 mAbs were able to successfully inhibit tumor growth and induced increased survival (Figure 2). Anti-4-1BB treatment resulted in the polyclonal expansion and differentiation of CD8+ T cells into effective tumor killers while the CD4+ T-cell depletion facilitated the infiltration of immune cells into the tumors and removed regulatory barriers such as Tregs.[²⁶]

Figure 2. Antitumor Effects of Combined Therapy with Anti-4-1BB and Anti-CD4 mAb in B16F10 Mouse Melanoma Model

Antitumor effects of combined therapy with anti-4-1BB and anti-CD4 mAb. B16F10 melanoma bearing mice 6 days after tumor cells sc injection (when the tumors were 3 to 5 mm in diameter) were injected i.p. with 100 μ g anti-4-1BB (3E1) and/or 400 μ g anti-CD4 (GK1.5), or 100 μ g rat IgG as a control, five times every 5 d.

PF-05082566 is a fully human IgG2 agonist monoclonal antibody targeting 4-1BB. The safety and tolerability of PF-05082566 is currently being evaluated in a Phase 1 study as a single agent in patients with advanced solid tumors or B cell lymphoma and in combination with rituximab in patients with CD20+ NHL (Study B1641001). PF-05082566, administered every 4 weeks, has been well tolerated (up to 10 mg/kg dose as single agent and up to 2.4 mg/kg in combination with rituximab) with mostly Grade 1 TEAEs attributed to PF-05082566.

Mogamulizumab is a humanized mAb of the IgG1/kappa isotype targeting CCR4-expressing cells approved in Japan for the treatment of relapsed or refractory CCR4 positive ATL, PTCL and CTCL and currently under investigation as single agent in patients with advanced solid tumors. Mogamulizumab demonstrated an acceptable safety profile. The AEs reported have generally been mild to moderate in severity, with the most frequent mogamulizumab-related TEAEs being infusion related reactions, nausea, pyrexia, fatigue, and drug eruption, all easily manageable through the administration of appropriate treatment.

Based on the upon consideration that show a potential synergies of the two agents this Phase 1b study will assess the safety and tolerability, establish the maximum tolerated dose (MTD) and the Recommended Phase 2 Dose (RP2D) of PF-05082566 in combination with mogamulizumab in patients with advanced solid tumors.

The Sponsor considers that the safety data in the ongoing Phase 1 First-In-Patient (FIP) study B1641001 and the published safety data for mogamulizumab support the development of the combination for the treatment of advanced cancers and the initiation of this Phase 1b clinical study B1641004. Study B1641001 will assess the safety and tolerability, as well as establish the maximum tolerated dose (MTD) and the Recommended Phase 2 Dose (RP2D) of PF-05082566 in combination with mogamulizumab in patients with advanced solid tumors. The available data support the benefit risk for the conduct of the trial, and the study includes monitoring and measures that potentially mitigate risks associated with the treatment.

2. STUDY OBJECTIVES AND ENDPOINTS

2.1. Objectives

Primary Objective

- To estimate the Maximum Tolerated Dose (MTD) and select the Recommended Phase 2 Dose (RP2D) of PF-05082566 in combination with mogamulizumab in patients with advanced solid tumors.

Secondary Objectives

- To evaluate the overall safety profile;
- To characterize the pharmacokinetics (PK) of PF-05082566 and mogamulizumab when given in combination;
- To evaluate the immunogenicity of PF-05082566 and mogamulizumab when given in combination;
- To document any anti-tumor activity.

CCI

- CCI

2.2. Endpoints

Primary Endpoint

- First 2 cycles Dose-Limiting Toxicities (DLTs).

Secondary Endpoints

- Adverse Events as characterized by type, frequency, severity [(as graded by National Cancer Institute Common Terminology Criteria for Adverse Events (NCI CTCAE v. 4.03)], seriousness and relationship to study therapy;
- Laboratory abnormalities as characterized by type, frequency, severity (as graded by NCI CTCAE v. 4.03);
- Vital Signs (blood pressure and pulse rate), weight, Eastern Cooperative Oncology Group (ECOG) Performance Status;
- PK parameters of PF-05082566 and mogamulizumab, including but not limited to C_{max} , C_{trough} , T_{max} , $AUC_{0\text{-last}}$, AUC_{tau} , $t_{1/2}$, CL and V_{ss} , as data permits;
- Anti-drug Antibody (ADA)/neutralizing antibody (Nab) titers for PF-05082566 and mogamulizumab;
- Objective tumor response (see [Appendix 2](#) and [Appendix 3](#) for details);
- Duration of response (DR) (expansion cohorts only);
- Time to response (TTR) (expansion cohorts only);
- Progression-free Survival (PFS) (expansion cohorts only).

CCI

- CCI

3. STUDY DESIGN

3.1. Study Overview

This is a Phase 1b, open-label, multi-center, multiple-dose, safety, PK and PD study designed to estimate the maximum tolerated dose (MTD), and select the Recommended Phase 2 Dose (RP2D) of PF-05082566 in combination with mogamulizumab in patients with advanced solid tumors.

This clinical study will include:

3.1.1. Dose-Finding portion

In the dose-finding portion, MTD of the combination will be estimated in patients with advanced solid tumors (ie, locally advanced or metastatic disease based on the TITE-CRM design^[28] and ^[33]) and according to the algorithm detailed in [Section 3.1.9](#).

PF-05082566 and mogamulizumab starting doses as well as the starting dose selection strategy are described in [Section 3.1.8](#).

A flat dosing of PF-05082566 100 mg will be studied to confirm the safety and PK at a dose that may be used for the expansion cohorts. This cohort will only enroll SCCHN and/or squamous NSCLC patients.

The 5.0 mg/kg cohort (if safe and tolerable) will enroll at least 6 squamous NSCLC patients.

It is estimated that approximately 30 patients would be required in the dose-finding portion to achieve the study objectives.

3.1.2. Dose Expansion portion

Once the MTD of PF-05082566 administered in combination with mogamulizumab has been estimated with confidence, expansion cohorts of patients will be enrolled to further study the safety, tolerability, PK/PD, and preliminary anti-tumor activity for PF-05082566 in combination with mogamulizumab, as well as to study [CC1](#)

Tumor types for the expansion cohorts will be selected from CRC, bladder, ovarian, squamous esophageal, SCCHN and/or squamous NSCLC. Dose, final tumor types, [CC1](#) for these cohorts will be selected based on emerging data from the dose-finding portion of the study or obtained from ongoing studies testing PF-05082566.

The total enrollment into all expansion cohorts will be up to 40 response-evaluable patients.

3.1.3. Study Treatment

In both portions, treatment will be administered in a 4-week cycles.

PF-05082566 will be administered as a 1-hour intravenous infusion (IV), every 4 weeks (q4wks), on Day 1 of each cycle. The starting dose of PF-05082566 will be 1.2 mg/kg.

Mogamulizumab will be given as a 1-hour IV infusion every week (qwk) for 4 consecutive weeks (Days 1, 8, 15 and 22) followed by biweekly dosing (Days 1 and 15), at the dose of 1 mg/kg.

On Day 1 of a dosing cycle, in which the drugs are co-administered, and PK samples are collected the mogamulizumab infusion will start 30 minutes (± 10 min) after completion of PF-05082566 infusion and after the end of infusion PF-05082566 PK blood sample and pre-mogamulizumab PK blood sample are drawn. See [Table 2](#).

Treatment with study drugs will continue until completion of 24 months of treatment (approximately 24 cycles), confirmed disease progression, patient refusal, unacceptable toxicity, whichever occurs first or the study is prematurely terminated by the Sponsor or one of the reasons for patient withdrawal listed (for details see [Section 6.4](#)).

Discontinuation from treatment may be considered at the investigator's discretion for patients who have attained a confirmed complete response (CR), and have received at least two cycles with mogamulizumab and PF-05082566 after the date the CR was confirmed. Patients who then experience radiologic disease progression will be eligible for re-treatment with both study drugs at the discretion of the investigator and by the approval of the Sponsor, if no anticancer treatment was administered since the last dose of study drugs, the patient meets the safety parameters listed in the Inclusion/Exclusion criteria, and the trial is still open. Patients will resume therapy at the same dose and schedule at the time of initial discontinuation.

Patients who completed the 24 months of treatment on-study and demonstrate clinical benefit with manageable toxicity and are willing to continue receiving the study treatment will be given the opportunity to continue treatment off-study upon agreement between investigator and Sponsor.

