ovarian, squamous esophageal, SCCHN and/or squamous NSCLC patients. Dose, tumor types, **CCI** for these cohorts will be selected based on emerging data from the dose-finding portion of the study or data obtained from ongoing studies testing PF-05082566.

The total enrollment into all expansion cohorts will be up to 40 response-evaluable patients.

Study Treatment

In both portions, treatment will be administered in 4-week cycles.

PF-05082566 will be administered as a 1-hour intravenous (IV) infusion, every 4 weeks (q4wks), on Day 1 of each cycle. The starting dose of PF-05082566 will be 1.2 mg/kg.

Mogamulizumab will be given as a 1-hour IV infusion, every week (qwk), for 4 consecutive weeks (Days 1, 8, 15 and 22) followed by biweekly dosing (Days 1 and 15), at the dose of 1 mg/kg.

On Day 1 of a dosing cycle, in which the drugs are co-administered, and PK samples are collected, the mogamulizumab infusion will start 30 minutes (± 10 min) after completion of PF-05082566 infusion and after the end of infusion PF-05082566 PK blood sample and pre-mogamulizumab PK blood sample are drawn. See [Table 2](#).

Treatment with study drugs will continue until completion of 24 months of treatment (approximately 24 cycles), confirmed disease progression, patient refusal, unacceptable toxicity, whichever occurs first, or the study is prematurely terminated by the Sponsor, or for one of the other reasons for patient withdrawal as specified in [Section 6.4](#).

Discontinuation from treatment may be considered at the investigator's discretion for patients who have attained a confirmed complete response (CR), and have received at least two cycles of mogamulizumab and PF-05082566 after the date the CR was confirmed. Patients who then experience radiologic disease progression will be eligible for re-treatment with both study drugs at the discretion of the investigator and by the approval of the Sponsor, if no anticancer treatment was administered since the last dose of study drugs, the patient meets the safety parameters listed in the Inclusion/Exclusion criteria, and the trial is still open.

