19. **Adverse Event (AE) Assessments:** Adverse events should be documented and recorded at each visit using NCI CTCAE version 4.03. Patients must be followed for AEs for 28 days after the last treatment administration or until all drug related toxicities have resolved, whichever is later; or earlier than 28 days should the patient commence another anticancer therapy in the meantime. For SAEs, the active reporting period begins from the time that the patient provides informed consent, through and including 60 calendar days after the last administration of the investigational products and before initiation of a new anti-cancer treatment. SAEs experienced by a patient after the active reporting period has ended should be reported to the Sponsor if the Investigator becomes aware of them; at a minimum, all SAEs that the Investigator believes have at least a reasonable possibility of being related to study drug are to be reported to the Sponsor. Pregnancy or breast feeding that occur during the trial, within 60 days of discontinuing treatment with mogamulizumab, or within 60 days after the cessation of PF-05082566 if the patient begins a new anticancer therapy, whichever is earlier, should be reported as stated in (see [Section 8.10](#), Exposure During Pregnancy for details).

20. **Concomitant Medications:** Concomitant medications will be recorded from 28 days prior to the start of study treatment and up to 28 days after the last dose of study treatment.

21. **Blood for PF-05082566 Pharmacokinetics:** Blood samples (2 mL whole blood at each time point) will be collected as follows:
Dose-finding cohorts: Cycles 1- 4 on Day 1 at pre-dose and at the end of PF-05082566 infusion; Cycle 5 on Day 1 at pre-dose, at the end of PF-05082566 infusion, and at 2, 6, 168 hrs. (Day 8) and 336 hrs. (Day 15) after the start of PF-05082566 infusion. Day 1 at pre-dose of Cycles 8, 12, 16, 20, 24 and at EOT. See [Section 7.3.1](#).
Expansion cohorts: the same PK schedule foreseen in the dose-finding portion will be followed for at least 10 patients in total from all expansion cohorts. For all other patients in the expansion cohorts, blood for PK will be taken on Cycle 1 Day 1 (at pre-dose and at the end of PF-05082566 infusion), Day 1 at pre-dose of Cycles 3, 5, 8, 12, 16, 20, 24 and at EOT. Timing of sampling may be modified based on emerging safety/PK data. See [Section 7.3.1](#).

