32. **Follow Up:** Patients should be evaluated up to 60 days for safety (SAEs) after last dose of study treatment. Refer to the protocol for specific guidelines. Patients continuing to experience drug related toxicity following discontinuation of study treatment will continue to be followed at least every 4 weeks until resolution or determination, in the clinical judgment of the Investigator, that no further improvement is expected. PK and immunogenicity samples should be collected as described in the PK and Immunogenicity **ASSESSMENTS** Section in SOA ([Table 2](#)).

Patients whose disease has not progressed at the end of treatment will enter into disease follow up. During this follow up period, patients will have disease assessments performed every 8 weeks (± 7 days). Once patients have exhibited disease progression or began a new anticancer therapy, or 6-month follow-up from the date of the last dose of the last enrolled patient, whichever occurs first, they will be withdrawn from the study. See [Section 4.3](#) for guidelines on contraception during this period.

Legend (X) = optional activity to be executed only if applicable; ADA= anti-drug antibodies; AE= adverse event; C=cycle; CRF= case report form; ECG= electrocardiogram; D=day; irRC= Immune-Related Response Criteria; PK=Pharmacokinetics;

TABLE OF CONTENTS

LIST OF TABLES	29
LIST OF FIGURES	29
APPENDICES	30
1. INTRODUCTION	31
1.1. Mechanism of Action/Indication	31
1.2. Background and Rationale	31
1.2.1. 4-1BB Target Biology and Mechanism of Action	31
1.2.2. Preclinical Profile of PF-05082566	32
1.2.2.1. In Vitro PF-05082566 Data	32
1.2.2.2. In Vivo Data: Functional Activity of PF-05082566	33
1.2.2.3. Preclinical Anti-Tumor Activity of PF-05082566	34
1.2.2.4. Preclinical Pharmacokinetics of PF-05082566	34
1.2.2.5. Pharmacokinetics and Pharmacodynamics Relationship of PF-05082566	34
1.2.2.6. Preclinical Toxicology of PF-05082566	35
1.2.3. Clinical Safety of PF-05082566	35
1.2.4. Clinical Efficacy of PF-05082566	38
1.2.4.1. Pharmacokinetics of PF-05082566 in Humans	39
1.2.4.2. Immunogenicity of PF-05082566	39
1.2.5. Mogamulizumab	40
1.2.5.1. Clinical Safety Data for Mogamulizumab	41
1.2.5.2. Pharmacokinetics of Mogamulizumab	43
1.2.5.3. Immunogenicity of Mogamulizumab	43
CCl	44
1.2.6. Study Rationale	44
2. STUDY OBJECTIVES AND ENDPOINTS	46
2.1. Objectives	46
2.2. Endpoints	47
3. STUDY DESIGN	48
3.1. Study Overview	48
3.1.1. Dose-Finding portion	48

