5.4. Administration

Study treatment administration should start no later than 7 days after registration.

A cycle is defined as the time from Day 1 dose to the next Day 1 dose of PF-05082566. If there are no treatment delays, a cycle will be 4 weeks in duration.

All trial treatments will be administered on an outpatient basis. After Cycle 1, study drugs may be administered up to 2 days before or after the scheduled treatment day of each cycle for administrative reasons. Patients will be observed in the clinic for at least 2 hours after the administration of study drug, throughout the duration of the study.

All patients should be weighed within 7 days prior to dosing for every cycle to ensure they did not experience either a weight loss or gain >10% from the prior weight used to calculate the amount of study drug required for dose preparation. Decision to recalculate the study drug dose based on the weight obtained at each cycle can be in accordance with institutional practice, however if the patient experienced either a weight loss or gain >10% compared to the weight used to calculate the initial dose, the amount of study drug required for preparation and administration for the current cycle must be recalculated using this most recent weight obtained.

As with any antibody, allergic reactions to dose administration are possible. Therefore, appropriate drugs and medical equipment to treat allergic or anaphylactic reactions must be immediately available, and study personnel must be trained to recognize and treat allergic and anaphylactic reactions. Patients should be instructed to report any delayed reactions to the Investigator immediately. If a patient experiences an infusion related reaction at any time during the study, premedication is recommended prior to subsequent infusions (see Section 5.4.2 for details on premedication to be used).

For both drugs, the exact duration of infusion should be recorded in both sources document and CRFs. The infusion rate should be reduced or interrupted in the case of symptoms of infusion reaction, and symptomatic treatment administered. The infusion may be continued at one-half the previous rate upon improvement of symptoms. If symptoms persist or worsen, the infusion should be discontinued.

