5.7.1. Prohibited Concomitant Medications

Medications or vaccinations specifically prohibited at study entry as specified in the exclusion criteria are also not allowed during the study treatment period, except for hematopoietic growth factors and steroids for symptomatic treatment (for details see [Section 5.8](#), Supportive Care).

If there is an important medical condition requiring any medication specifically prohibited during the trial, discontinuation from study treatment may be considered. The investigator should discuss the proposed course of action with the Sponsor Clinical Lead and/or Medical Monitor. The final decision on any supportive therapy or vaccination rests with the investigator and/or the patient's primary physician. However, the decision to continue the patient on study treatment requires the mutual agreement of the Investigator, the Sponsor, and the patient.

Patients are prohibited from receiving the following therapies during the Screening and Treatment Phase (including retreatment for post-complete response relapse) of this clinical protocol:

- Anti-cancer systemic chemotherapy or biological therapy.
- Immunotherapy not specified in this protocol.
- Investigational agents other than mogamulizumab or PF-05082566.
- Live vaccines (flu vaccination allowed).
- Glucocorticoids for any purpose other than to modulate symptoms from an event of clinical interest of suspected immunologic etiology, except as agreed upon by the Sponsor.

Consider withholding or discontinuing concomitant therapy with monoclonal antibodies of the same subclass as the study drugs (ie, IgG_K and IgG2) in patients where anti-study drug antibodies are detected while on-study.

The concurrent use of vitamins or herbal supplements should be considered with caution.

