6.3. Follow-up Visit

For follow-up procedures, see [Schedule of Activities](#) and [ASSESSMENTS](#) Sections.

Patients continuing to experience treatment-related toxicity following discontinuation of study treatment will continue to be followed at least every 4 weeks until resolution or determination, in the clinical judgment of the Investigator, that no further improvement is expected.

Only those patients whose disease has not progressed at the end of treatment will enter into disease follow-up. During this follow-up period, patients will have disease assessments performed every 8 weeks \pm 7 days. Once patients have exhibited disease progression or began a new anti-cancer therapy (not including radiotherapy to a non-target tumor lesion), whichever occurs first, the date of progression or that of the new anticancer therapy initiation will be recorded on the appropriate CRF page, and the patients will be withdrawn from the study. No further data will be collected from these patients.

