6.4. Patient Withdrawal

Patients may withdraw from treatment at any time at their own request, or they may be withdrawn at the discretion of the investigator or Sponsor for safety or behavioral reasons, or the inability of the patient to comply with the protocol-required schedule of study visits or procedures at a given study site.

Reasons for discontinuation of study treatment may include:

- Disease progression according to RECIST v. 1.1 ([Appendix 2](#)) and/or irRC ([Appendix 3](#)) (see [Section 5.4.5](#) for details and exceptions);
- Patients who have achieved a confirmed CR, and have had at least two additional cycles of mogamulizumab and PF-05082566 after the date the CR was confirmed;
- Global deterioration of health status requiring discontinuation;
- Unacceptable toxicity;
- Pregnancy;
- Significant protocol violation;
- Lost to follow-up;
- Patient refused further treatment (follow up permitted by the patient);
- Consent withdrawal (cessation of follow up);
- Study terminated by Sponsor;
- Death.

Reasons for withdrawal from study follow-up may include:

- Completed study follow-up;
- Study terminated by Sponsor;

- Start of another anticancer therapy;
- Refusal for further follow-up;
- Lost to follow-up;
- Death.

If a patient does not return for a scheduled visit, every effort should be made to contact the patient. All attempts to contact the patient and information received during contact attempts must be documented in the patient's medical record. In any circumstance, every effort should be made to document patient outcome, if possible. The investigator should inquire about the reason for withdrawal, request the patient return for a final visit, if applicable, and follow-up with the patient regarding any unresolved AEs.

If the patient refuses further visits, no further study specific evaluations should be performed, and no additional data should be collected. The Sponsor may retain and continue to use any data collected before such withdrawal of consent.

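### The protocol allows on-study re-treatment at relapse after a complete-response stop but withdraws the same patient at that relapse, and the SAP has no rule for the drug-free gap if re-treatment doses are recorded as further cycles

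*Protocol*

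**What the plan says.** **Re-treatment is allowed, on study.** Protocol 3.1.3, 5.4.4 and the summary let a patient stop after a confirmed CR and at least two further cycles. If the disease then progresses: "Patients who then experience radiologic disease progression will be eligible for re-treatment with both study drugs at the discretion of the investigator". The conditions are Sponsor approval, no anticancer treatment since the last study dose, the eligibility safety parameters and an open trial. Dose and schedule are those in force at the stop. Section 5.7.1 covers the "Treatment Phase (including retreatment for post-complete response relapse) of this clinical protocol", which places re-treatment on study. Off-study continuation is reserved for patients who complete 24 months.

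**The same event ends participation.** A patient who stops in CR has not progressed at end of treatment and so enters disease follow-up under 6.3. At progression, 6.3 says "the patients will be withdrawn from the study. No further data will be collected from these patients". Footnote 32 gives the same consequence: "whichever occurs first, they will be withdrawn from the study". Neither mentions re-treatment. The exceptions that 6.4 refers to are in 5.4.5, which covers treatment past an initial progression, not relapse after a CR stop.

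**The SAP is silent on re-treatment.**
- 3.4.1: the last dose is the latest non-zero dose of either drug.
- 3.5.1 and 5.2.7: the on-treatment period runs from first dose to 30 days after last dose, or to the day before new anti-cancer drug therapy if earlier.
- 6.5.3: every cycle but the last ends the day before the next one starts.
- 6.5.3.1 and 6.5.3.2: the dose-intensity denominator runs from first dose to the end of the last dosed cycle.
- 6.5.3.4: dose delay is taken between consecutive non-zero doses.

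**The concern.** The event that opens re-treatment is the event that triggers withdrawal. A site that follows 6.3 to the letter could dose a patient with two investigational antibodies while collecting nothing on the CRF.

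A site that records the doses as further cycles avoids that problem and meets a different one. The SAP rules run from first dose to last dose without a break, so weeks deliberately spent off drug count as treatment. A fully dosed patient then looks under-dosed, exposure looks longer than it was, and events well after the first course can be classed as treatment-emergent. For any one patient these two outcomes are alternatives.

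**Working it through.** The documents give no figure for this point, so the check applies the SAP formulas to an assumed calendar.

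**Assumptions (not in the documents).** Eight full-dose cycles, a CR stop, a drug-free gap of G weeks beyond the normal 28 days, then four full-dose cycles entered as cycles 9-12. Eight cycles is feasible: 8 weeks to the first scan, 4 to confirmation and 8 for two further cycles make 20 weeks, or 5 cycles.

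**Formulas**
- Four-week periods in the denominator: N = 8 + G/4 + 4.
- PF-05082566 RDI = 12/N.
- Mogamulizumab given (d = dose per infusion): 4d + 7×2d + 4×2d = 26d. Intended, with n1 = 1: 4d + (N − 1)×2d. RDI is the ratio.
- PF-05082566 exposure = (last dose − first dose + 28)/7 = 4N weeks.
- Cycle 8 duration = (28 + 7G)/7 weeks.
- Dose delay, either drug, keeping the usual 28- or 14-day planned interval: 7G days.
- Excess on-treatment days: the last initial-course dose is C8D15, 14 days after C8D1, so the window should close 44 days after C8D1. Re-treatment starts 28 + 7G days after C8D1. Excess = 28 + 7G − 44 − 1 = 7G − 17.

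| Quantity | Without gap | G = 8 | G = 24 | G = 52 |
|---|---|---|---|---|
| N | 12 | 14 | 18 | 25 |
| PF-05082566 RDI | 100% | 12/14 = 85.7% | 12/18 = 66.7% | 12/25 = 48.0% |
| Mogamulizumab RDI | 100% | 26/30 = 86.7% | 26/38 = 68.4% | 26/52 = 50.0% |
| PF-05082566 exposure (weeks) | 48 | 56 | 72 | 100 |
| Cycle 8 (weeks) | 4 | 12 | 28 | 56 |
| Dose delay (days) | 0 | 56 | 168 | 364 |
| Excess on-treatment days | 0 | 39 | 151 | 347 |

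The 52-week gap is near the ceiling, because 5.4.4 counts 24 months (104 weeks) from Cycle 1 Day 1.

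**Why the window stays open.** New anti-cancer drug therapy would close it, but re-treatment requires that none was given.

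**Which events are reclassified.** Only those collected. Footnote 19 says "Patients must be followed for AEs for 28 days after the last treatment administration", or until drug-related toxicity resolves if later, and takes SAEs to 60 days. The well-supported part is therefore SAEs on days 31-60, 30 days of the gap. Section 8.2 has AEs recorded through the last visit; only on that reading could all AEs across the full excess window count.

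**Check of the remedy.** With separate courses, PF-05082566 gives 8/8 and 4/4, and exposure is 32 + 16 = 48 weeks. Mogamulizumab gives 18d/18d in the first course. In the second, n1 = 0 gives 8d/8d = 100%. Leaving n1 = 1 would give 8d/(4d + 3×2d) = 80%, because weekly loading is not repeated.

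**The case against.** The re-treatment text is specific and needs Sponsor approval, whereas 6.3 is a general follow-up rule, and the specific rule should prevail. Section 5.7.1 supports that. Section 6.4, under "Reasons for withdrawal from study follow-up may include", does not name progression, though its list is not exhaustive. Section 5.4 requires recording: "For both drugs, the exact duration of infusion should be recorded in both sources document and CRFs". This largely stands. A reader might infer that safety data on re-treated patients will be lost; the documents support only a risk from conflicting instructions.

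The SAP half rests on a chain: CR, stop, relapse, approval, and entry as consecutive cycles. The last link depends on the eCRF. Section 5.4.8 counts a restart after Day 28 as Day 1 of the next cycle, but it concerns interruptions, so it helps only by analogy. A reader might infer that RDI is wrong for any re-treated patient; it is wrong only if the doses are recorded that way.

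The dose-delay figure is partly convention. The SAP does not define the planned interval across a permitted stop, and all three delays fall in its category of 7 or more days. Counting late SAEs as treatment-emergent is also conservative.

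None of this removes the missing exception in 6.3 and footnote 32 or the missing SAP rule.

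**Conclusion.** The point holds as a minor one. The conflict between the re-treatment text and 6.3 with footnote 32 is direct and rests on wording alone. The SAP effect is conditional on how re-treatment doses are recorded. At a 24-week gap it lowers RDI to about 67% and 68%, extends PF-05082566 exposure to 72 weeks, and makes events collected more than 30 days after the last initial-course dose treatment-emergent. These sizes depend on the assumed calendar.

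Three stronger readings are not supported. The two harms do not add up, since unrecorded doses never reach the SAP formulas. The 151-day excess should not be read as 151 days of reclassified events, because that needs all AEs to be collected throughout the gap. The number of patients affected cannot be projected: the documents give no combination response data, and the single-agent results in B1641001 do not supply a rate.

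Only descriptive exposure and TEAE summaries change, for few or no patients. DLTs are confined to the first two cycles, so the MTD is untouched. RECIST v1.1 BOR, DR and PFS are settled at the first documented progression and do not change.

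**What to change.** **Protocol.** In 6.3 and footnote 32, add one sentence each: patients approved for re-treatment after a CR stop are not withdrawn at progression, and Table 1 dosing, AE/SAE and laboratory collection continues for them.

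**SAP.** In 3.5.1, 5.2.7 and 6.5.3, treat the initial and re-treatment courses as separate periods. Close the first on-treatment period 30 days after that course's last dose and reopen it at the first re-treatment dose. Exclude the gap from cycle duration, exposure duration, DI/RDI and dose delay. For re-treatment, set intended mogamulizumab dosing to biweekly only (n1 = 0), since therapy resumes on the schedule in force at the stop.

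**Cost.** Two protocol sentences, a few lines of SAP text, and minor programming needed only if a patient is re-treated. No extra patients; re-treated patients follow the existing Table 1 treatment visits.
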